## 6. Randomization

After sample size calculation and selection of the sample according to the inclusion criteria, the patients were randomized to one of the two treatments (TENS or PBM) using an allocation software (<https://www.graphpad.com/quickcalcs/randomize1/>). This program did not randomly choose a treatment for each patient but randomly shuffled a defined number of patients among a defined number of treatment slots.

## 7. Blinding

Blinding was not possible since the devices used for the interventions performed in the study and control groups were different.

## 8. Statistical analysis

All data were analyzed using the Statistical Package for the Social Sciences 25.0 (SPSS). First, the collected data were submitted to descriptive analysis. Fisher's exact test was then used to determine whether statistically significant differences in systemic alterations, psychiatric disorders and medication use exist at T0 between the TENS and PBM groups.

The quantitative data (VAS score and unstimulated salivary flow) were analyzed using the Kolmogorov-Smirnov normality test to assess if the data are normally distributed, which

was confirmed based on the mean error. Two-factor ANOVA was used to analyze intergroup (TENS and PBM) and intragroup (repeated measures at T0, T1, T2 and T3) differences in mean VAS scores and unstimulated salivary flow. For this purpose, the assumptions of sphericity were tested using the Mauchly test. The post-test of intergroup and intragroup interactions was carried out based on Bonferroni corrections, as well as using the trend test of the interaction between time and intervention. A level of statistical significance of 95% was adopted for all tests.

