#### 4. Outcomes

Pain/burning was the primary outcome and was measured on a visual analogue scale (VAS; 0-10 cm). The patients were asked to choose a number from 0 to 10 on the scale to describe the level of intensity of their symptoms.

Changes in unstimulated salivary flow, xerostomia, and dysgeusia were the secondary outcomes. Saliva was collected as described by Navazesh and Kumar [26] and patients with an unstimulated salivary flow rate  $< 0.1$  ml/min were classified as having hyposalivation.

Information on xerostomia was collected according to the method of Murray Thomson et al. (2006) using a standard question and the Xerostomia Inventory (XI). Patients answered the following question: "How often does your mouth feel dry?" (response options: "never", "occasionally", "frequently", "always"). On each occasion, those who gave either of the latter two responses were categorised as xerostomic. The XI was used to obtain information on the severity of xerostomia symptoms, being an 11-item summated rating scale which combines the responses to 11 individual items into a single continuous scale score which represents the severity of chronic xerostomia, and higher scores represent more severe symptoms. The patients were asked to choose one of five responses ("never", scoring 1; "hardly ever", 2; "occasionally", 3; "fairly often", 4 and "very often", 5) to the following statements referring to the previous 4 weeks: "my mouth feels dry"; "my lips feel dry"; "I get up at night to drink"; "my mouth feels dry when eating a meal"; "I sip liquids to aid in swallowing food"; "I suck sweets or cough lollies to relieve dry mouth"; "my throat feels dry"; "the skin of my face feels dry"; "my eyes feel dry"; "my lips feel dry" and "the inside of my nose feels dry". Each individual's responses were scored and summed to give a single XI score.

Dysgeusia was analyzed using an adaptation of the method proposed by Muller et al. [28], in which the four basic tastes at four different concentrations are tested. Urea was used as bitter taste as proposed by Henn et al. [29] (sucrose solution: 0.4 g/mL, 0.2 g/mL, 0.1 g/mL, 0.005 g/mL; sodium chloride: 0.25 g/mL, 0.1 g/mL, 0.04 g/mL, 0.016 g/mL; citric acid: 0.3 g/mL, 0.165 g/mL, 0.09 g/mL, 0.05 g/mL; urea: 0.005 g/mL, 0.04 g/mL, 0.02 g/mL, 0.01 g/mL). Filter paper strips were impregnated with the test solutions as proposed by Kettenmann et al.

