[30]. The strips were placed in the center of the tongue and the patient was asked to identify the taste. The 10th percentile was used to define the presence or absence of dysgeusia.

The primary and secondary outcomes were collected at baseline (T0), after the 4th treatment session (T1), after the 8th treatment session (T2), and 30 days after the end of treatment (T3).

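### Xerostomia is a declared secondary outcome with a continuous score (XI) collected at four visits, but section 8 plans no TENS-versus-PBM comparison of it beyond general descriptive analysis

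*Combined protocol and SAP*

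**What the plan says.** Section 4 (Outcomes) states: "Changes in unstimulated salivary flow, xerostomia, and dysgeusia were the secondary outcomes". Xerostomia is measured in two ways, "using a standard question and the Xerostomia Inventory (XI"). The standard question has four response levels, and "those who gave either of the latter two responses were categorised as xerostomic". The XI "combines the responses to 11 individual items into a single continuous scale score which represents the severity of chronic xerostomia". Section 4 also fixes the visits: "The primary and secondary outcomes were collected at baseline (T0"), then at T1, T2 and T3.

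Section 8 (Statistical analysis) opens with descriptive analysis of the collected data. It then applies Fisher's exact test to three patient characteristics (systemic conditions, psychiatric disorders, medication) at T0. For measured outcomes it says "The quantitative data (VAS score and unstimulated salivary flow) were analyzed" for normality, and it describes the two-factor ANOVA as examining "differences in mean VAS scores and unstimulated salivary flow". No other between-group test of an outcome is named.

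**The concern.** Section 8 names its quantitative variables explicitly, and names the same two again for the ANOVA. The XI is in neither place, although section 4 defines it as continuous. Salivary flow, another secondary outcome, gets a full group-by-time analysis; xerostomia gets no model, visit or contrast.

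Two things are at stake. First, a declared outcome would be collected four times and not compared between arms. Second, if someone does compare it, the choice between the XI and the question, the visit and the test are all open and could be made with the results in view. That choice has consequences, because a four-level answer cut to yes/no loses information in a trial of 28 patients. A patient who is not classed as xerostomic at T0 also cannot improve on the yes/no measure.

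**Working it through.** **Step 1. Outcomes set against planned analyses.** The plan gives no power or precision figure for xerostomia, so there is none to reproduce; section 5 sizes the trial on VAS alone.

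| Measure (section 4) | Type | Visits | Between-arm analysis in section 8 |
|---|---|---|---|
| VAS (primary) | quantitative | T0-T3 | two-factor ANOVA |
| Unstimulated salivary flow | quantitative | T0-T3 | two-factor ANOVA |
| XI score | continuous | T0-T3 | none named |
| Dry-mouth question | four levels, cut to yes/no | T0-T3 | none named (Fisher's test covers T0 characteristics only) |

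The omission follows from the text alone and needs no assumption.

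**Step 2. The XI item list.** Eleven statements are printed, but the one about dry lips appears twice, leaving 10 distinct items. Eleven items scored 1 to 5 give a range of 11 to 55. If the repeat is a printing slip, one item is missing from the text. If the form was used as printed, lips count twice.

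**Step 3. What the choice of measure would cost.** Inputs:
- 28 patients in two groups (section 5); n = 14 per arm assumes an equal split and no losses.
- Two-sided alpha 0.05 (section 8 gives the level but not the sidedness).
- True shift d = 0.70 or 0.80 SD. The documents give no XI effect; 0.70 is borrowed from the VAS calculation in section 5, and 0.80 is an assumption.
- Correlation of T0 XI with follow-up XI: r = 0.5 to 0.7, assumed.
- For the yes/no version, the same underlying normal score cut so that 60% of the comparison arm is xerostomic, assumed.

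Unadjusted t-test: noncentrality = d x sqrt(n/2) = d x sqrt(7), with 26 df and critical value 2.056.
- d = 0.70: 0.70 x 2.646 = 1.85, power 43%.
- d = 0.80: 0.80 x 2.646 = 2.12, power 53%.

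T0-adjusted: replace d by d / sqrt(1 - r^2).
- d = 0.70: 0.70/0.866 = 0.81, power 54% (r = 0.5); 0.70/0.714 = 0.98, power 70% (r = 0.7).
- d = 0.80: 0.80/0.866 = 0.92, power 65% (r = 0.5); 0.80/0.714 = 1.12, power 81% (r = 0.7).

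Yes/no by Fisher's exact test: the rate in the better arm is Phi(Phi^-1(0.60) - d), and exact power sums over all pairs of counts with p <= 0.05.
- d = 0.70: 60% against 33%, power 17%.
- d = 0.80: 60% against 29%, power 23%.

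The assumed cut matters little: at d = 0.80, comparison-arm rates from 40% to 80% give 21% to 24%. In counts, 12/14 against 6/14 gives p = 0.046, while 11/14 against 6/14 gives p = 0.12.

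**Step 4. Precision.** The half-width of the 95% CI, in SD of the score, is about 2.056 x sqrt(2/14) = 0.78 unadjusted. Adjusted (25 df, critical value 2.060), it is 2.060 x 0.378 x 0.866 = 0.67 at r = 0.5 and 2.060 x 0.378 x 0.714 = 0.56 at r = 0.7.

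**The case against.** The strongest reply is that the gap is partly covered. The general descriptive analysis could summarise XI by arm and visit, and salivary flow, the objective measure nearest to dry mouth, is in the ANOVA. Both points stand, so it would be wrong to say that the XI cannot be used at all. But a descriptive summary is not a stated contrast with an interval, and flow is listed as an outcome separate from xerostomia.

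A reader might infer that xerostomia is to be compared only as yes/no with Fisher's test. The documents do not say so, because that test is limited to T0 characteristics. The Fisher power figures therefore describe a possible fallback and not a planned analysis. They are also approximate: the yes/no item is a separate question, not a cut of the XI.

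A reader might also set the T0-adjusted figures against Fisher's test and credit the whole difference to the XI. Part of it comes from the adjustment. Like for like, the comparison is 43% against about 17% at 0.7 SD, and 53% against about 23% at 0.8 SD.

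It is tempting to argue that dry mouth is where TENS should differ from PBM, because the electrodes sit beside the salivary glands. The documents state no such hypothesis, and the point does not need it.

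Finally, adding the XI to the existing ANOVA would also close the gap. That is true; a T0-adjusted contrast at named visits is preferred for its precision and clear estimate, but it is not the only acceptable model.

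**Conclusion.** The point holds as an omission: a declared secondary outcome with a continuous measure at four visits has no planned between-arm comparison beyond general description. This is certain from sections 4 and 8.

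The size of the consequence is conditional. With 14 per arm, two-sided 0.05 and a 0.7-0.8 SD shift, power is 43-53% for the unadjusted score and 54-81% with T0 adjustment at a correlation of 0.5-0.7. It would be about 17-23% if analysts fell back on yes/no. The equal split, shift, correlation and cut are assumptions. The XI makes better use of the data, but power remains limited on most of these settings, so the interval is the main product.

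The primary VAS analysis is unaffected. The change should be made, but the trial's main conclusion does not depend on it.

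**What to change.** 1. Check the XI form actually used against the printed list, resolve the repeated item, and state the scoring range.
2. Add the XI score to the quantitative outcomes in section 8. Report the TENS-PBM difference at T2 and at T3, adjusted for T0 XI, each with a 95% CI.
3. Keep the four-level question as supportive, and state how it will be analysed.
4. Section 1 dates the patients from April 2021 to February 2022. If the comparison is added after data collection, label it post hoc.

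Dysgeusia, also a secondary outcome, has no named between-arm analysis either, and the same edit could deal with it.

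The cost is a short addition to section 8, one more model and one more secondary comparison to interpret. No further patients, visits or measurements are needed.

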## 5. Sample size

The sample size was calculated according to Sikora et al. [31] who compared the efficacy of PBM to a placebo group (laser off). In that study, the mean and standard deviation (SD) of the VAS score in the placebo group at the end of treatment was  $2.417 \pm 2.918$ . Considering that acceptable improvement in the PBM group would be at least 10% after the intervention, we obtained an effect value ( $E$ ) = 2.17. The sample size was then calculated using a t-test for comparing the means of continuous variables, whose standardized effect size was 0.70 assuming a one-sided alpha error of 0.05 and a beta error of 0.20, resulting in 28 patients divided into two intervention groups.

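### Baseline VAS is an outcome level and not a covariate in the planned ANOVA: the group main effect shrinks to 75%, the main, interaction and trend tests are all exposed to chance T0 imbalance, and none is named as deciding

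*Combined protocol and SAP*

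**What the plan says.** Section 4 (Outcomes) makes VAS pain/burning primary without naming a deciding visit. On timing it says "The primary and secondary outcomes were collected at baseline (T0"), then after the fourth session (T1), after the eighth (T2) and 30 days post-treatment (T3). Under section 6 (Randomization), "the patients were randomized to one of the two treatments (TENS or PBM"); no stratification on baseline VAS is mentioned.

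Section 8 (Statistical analysis) sets the model for VAS and salivary flow: "Two-factor ANOVA was used to analyze intergroup (TENS and PBM) and intragroup (repeated measures at T0, T1, T2 and T3) differences". T0 is thus one of four levels of the repeated factor. No covariate is mentioned, and the Fisher tests at T0 cover systemic alterations, psychiatric disorders and medication, not VAS. On follow-up tests: "The post-test of intergroup and intragroup interactions was carried out based on Bonferroni corrections, as well as using the trend test of the interaction"; the interaction meant is group by time. On the level: "A level of statistical significance of 95% was adopted for all tests". On the covariance assumption, "the assumptions of sphericity were tested using the Mauchly test", with no statement of what follows if sphericity fails.

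**The concern.** A pre-treatment measurement cannot show a treatment effect. Averaging it into the group comparison pulls the estimate towards zero and brings in whatever difference the shuffle of 28 patients happened to leave at T0. The interaction and trend tests use T0 as the reference for change, so the same chance difference reaches them through regression to the mean. The measured T0 VAS could remove this but is not used for that purpose.

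The plan also leaves open which result answers the trial's question. Main effect, interaction and trend are all judged at one level, and the Bonferroni correction is attached to the post-tests, not to the choice among these three. At stake are precision, protection against an unlucky baseline, and freedom to choose the result after seeing it, in a small unblinded trial.

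**Working it through.** **Inputs.** From the documents: visits T0-T3 (section 4), 28 patients and 0.70 SD (section 5), the model and tests (section 8). Assumed, because the documents do not give them: 14 per arm, normal equal-variance scores, two-sided 5%, and within-patient correlation either compound symmetric (CS, rho = 0.3/0.5/0.7) or AR(1) (adjacent correlation 0.5/0.7/0.85). Triples below follow that order.

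**The plan's own figure.** Section 5 gives "standardized effect size was 0.70 assuming a one-sided alpha error of 0.05 and a beta error of 0.20, resulting in 28 patients". A two-sample comparison needs 2(1.645 + 0.842)²/0.70² = 25.2, so 26 per arm (52 in total) after rounding up; the t-test version also gives 26. The stated 28 is not reproduced. That is a separate issue, and 28 is used here only as the planned size. The 0.70 comes from a study "who compared the efficacy of PBM to a placebo group (laser off"), not from TENS versus PBM, so the power figures are illustrative.

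**Dilution.** With group differences (0, d1, d2, d3) at T0-T3, the main effect is (0 + d1 + d2 + d3)/4 = 0.75 × mean(d1, d2, d3). This needs no assumption on SD, correlation or sample size. For a constant 0.70 SD it is 0.525 SD. Under CS its standard error is √[(2/14)(1 + 3rho)/4] = 0.260/0.299/0.333. For the unadjusted T1-T3 average it is √[(2/14)(1 + 2rho)/3] = 0.276/0.309/0.338. The estimate falls by 25% and its standard error by only 6/3/2%, so power is lost.

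**Chance imbalance.** The T0 difference b has standard deviation √(2/14) = 0.378 SD, so P(|b| ≥ 0.5 SD) = 2[1 − Φ(0.5/0.378)] = 0.19. Under CS, b shifts the main effect by b(1 + 3rho)/4 = 0.475b/0.625b/0.775b. It shifts the change from T0 by −(1 − rho)b = −0.7b/−0.5b/−0.3b. Adjusting for T0 removes both shifts. Simulated false positives in the trials with |b| ≥ 0.5 SD and no treatment effect (accurate to about one percentage point):

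| Test | CS 0.3/0.5/0.7 | AR(1) 0.5/0.7/0.85 |
|---|---|---|
| Main effect | 16/20/24% | 16/19/23% |
| Interaction, uncorrected | 11/9/8% | 15/15/12% |
| Trend | 12/10/8% | 15/13/10% |
| T0-adjusted contrast | 5% | 5% |

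**All trials together, no effect.** Each test holds about 5%, except the uncorrected interaction under AR(1), at 5.7/6.3/6.8%. Claiming either the main effect or the interaction gives about 10% under CS and 10-12% under AR(1).

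**Power, CS, 0.70 SD.** The interaction has noncentrality (14/2) × SS/(1 − rho), where SS is the sum of squared deviations of the profile from its own mean. SS is 0.75 × 0.70² = 0.3675 both for a constant T1-T3 effect and for an effect at T2 only. The noncentrality is therefore 3.675/5.145/8.575 on F(3, 78) in either case.

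| Test | Constant T1-T3 | T2 only | Linear to 0.70 at T3 |
|---|---|---|---|
| Main effect | 49/40/33% | | |
| Interaction | 32/43/66% | 32/43/66% | |
| Trend | 30/39/59% | | 36/47/68% |
| T1-T3 average, unadjusted | 69/59/51% | | |
| T1-T3 average, adjusted | 75/77/88% | 14/15/18% | 42/44/55% |
| T2, unadjusted | 43/43/43% | 43/43/43% | |
| T2, adjusted | 45/52/69% | 45/52/69% | |

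For a constant effect, going from the main effect to the unadjusted T1-T3 average gains 20/19/18 points. Adjusting for T0 then adds 6/18/37.

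**The case against.** The strongest defence is that the group-by-time interaction is the natural test of a treatment effect in this design, and that it is not diluted. That is correct, and the 75% factor must be confined to the main effect. But section 8 does not name the interaction as deciding and explicitly includes the intergroup comparison. Nor is the interaction immune to T0 imbalance: at AR(1) 0.5 it does about as badly as the main effect (15% against 16%).

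A second defence is that the Bonferroni post-tests may include group comparisons at single visits. Read that way, they are undiluted, with about 43% power each before correction. This stands, but it adds to the list of claimable tests and does not settle which one decides.

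Third, the power argument can be overstated. The gain of the adjusted T1-T3 average over the main effect is not all due to adjustment: at correlation 0.3, 20 of the 26 points come from dropping T0 and averaging. The average is also a choice of estimand. It loses clearly if the effect is at T2 only, and it loses to the trend test at CS 0.5 and 0.7 if the effect rises linearly. Section 5 sizes the trial on end-of-treatment VAS, which points to T2. All of this stands, and it limits the remedy to adjusting for T0 and naming a contrast.

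A reader might infer that the ANOVA is invalid or inflates the false-positive rate in general. The documents do not support that: over all trials each test holds about 5%, with a modest excess only for the interaction if sphericity fails and nothing is corrected. Nor do they show that T0 was in fact unbalanced or that a result was picked, since they report no outcome data.

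**Conclusion.** The point holds as a matter of efficiency, chance imbalance and an unnamed deciding test; it should be fixed but does not invalidate the analysis. The 75% factor is algebra and rests only on a zero expected T0 difference. The absence of a T0 covariate and of a deciding test is plain from section 8. The other sizes rest on the stated assumptions: false positives of roughly 8-24% for the planned tests in the one trial in five with a T0 difference of at least 0.5 SD, against 5% after adjustment, and about 10-12% overall if either main effect or interaction may be claimed. The direction is the same under both correlation structures, but the gap between main effect and interaction depends on the correlation, which the documents do not give. The case for adjusting for T0 is firm. The documents do not establish that one particular adjusted contrast is best.

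**What to change.** Compare the groups on post-treatment VAS with T0 VAS as covariate. Use either an ANCOVA or a repeated-measures model of T1-T3 with group, visit, group-by-visit, T0 and T0-by-visit. With complete data, an ANCOVA of the T1-T3 mean gives the same estimate of the average as the fuller model. Name one T0-adjusted contrast, with its 95% CI, as the primary result. Label the main effect, interaction, trend and Bonferroni post-tests supportive, and state what is done if sphericity fails.

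The choice of contrast is a trade-off for the sponsor. The T1-T3 average is stronger for a sustained effect. The T2 difference matches the end-of-treatment VAS used in section 5, but for a constant effect it is 4 points below, 9 above and 3 above the best planned test at CS 0.3/0.5/0.7. Its main benefit there is protection from T0 imbalance.

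The text is in the past tense and section 1 dates the study to February 2022, so the results are probably known. A contrast named now is not pre-specified: disclose the change as a re-analysis and report both the adjusted average and the adjusted T2 difference.

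The cost is no new data, a few lines of SPSS syntax, and one degree of freedom in the simple ANCOVA (one T0 slope per visit in the repeated-measures model).

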### 2. Participants

Patients older than 18 years who had a burning or dysesthetic sensation in the oral mucosa that recurred daily for more than 2 hours per day for more than 3 months, in the absence of clinically evident causal lesions [4], were included in the study. We also included patients with hyposalivation or any systemic alteration that could be related to a burning sensation in the oral mucosa but who did not have clinical alterations in the oral mucosa such as erosive lichen planus, geographic tongue, infections, allergic reactions, trauma, or injuries caused by physical or chemical agents. Patients who did not comply with the treatment protocol of the study were excluded from the sample.

Before the beginning of treatment, clinical and sociodemographic data of the patients were collected and blood tests were requested (complete blood count, fasting blood glucose, total cholesterol and fractions, triglycerides, ferritin, vitamin B12, folic acid, zinc, thyroxine, triiodothyronine, and antinuclear antibodies).

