### 3. Interventions

In the study group, a portable TENS 7000 device (Roscoe Medical, Middleburg Heights, OH, USA) was used for stimulation. The device was calibrated for a frequency of 50 Hz and its intensity was modulated according to the patient's comfort (pulse amplitude of 1-4). Each session lasted 25 minutes. The self-adhesive electrodes were connected to the channels of the device and **attached to the patient's skin** of both facial sides next of the major salivary glands (parotid and submandibular glands), passing through the mandibular branch of the trigeminal

nerve as shown in figure 1. The patients were submitted to the respective treatment protocol once a week for eight consecutive weeks, totaling 8 treatment sessions.

In the control group, photobiomodulation was applied using a laser whose parameters are represented in table 1. During laser application, the patients and the clinician wore the protective glasses (figure 2).

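### The planned repeated-measures ANOVA drops any patient with a missing visit, chiefly treatment completers who miss T3, which costs precision and can bias the change over time

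*Combined protocol and SAP*

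**What the plan says.** Section 8 (Statistical analysis) gives one model for VAS, the primary outcome, and for unstimulated salivary flow: "Two-factor ANOVA was used to analyze intergroup (TENS and PBM) and intragroup (repeated measures at T0, T1, T2 and T3) differences". It adds that "the assumptions of sphericity were tested using the Mauchly test". The software is SPSS 25.0, and post-tests are Bonferroni-corrected.

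Section 3 (Interventions) sets treatment at "once a week for eight consecutive weeks, totaling 8 treatment sessions". Section 4 (Outcomes) places T1 after session 4 and T2 after session 8. T3 comes "30 days after the end of treatment (T3"), once weekly contact has stopped.

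On who is analysed, section 2 (Participants) says only: "Patients who did not comply with the treatment protocol of the study were excluded from the sample". Section 5 (Sample size) arrives at 28 patients in two groups and mentions no allowance for loss. No section names a missing-data rule, imputation, a mixed model or an analysis population.

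**The concern.** Mauchly's test checks the covariance of a complete set of repeated measurements within patients. A two-factor ANOVA accompanied by it is the classical procedure, which needs a value at every level of the time factor. If one of T0, T1, T2 or T3 is missing, the whole patient goes, including values already collected.

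This differs from the section 2 exclusion, which concerns compliance with treatment. A patient who attends all 8 sessions and then does not return for T3 has complied with treatment, and section 2 does not say how that patient is handled. The method removes the patient without the plan saying so.

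Two things are at stake. One is precision, in a trial where each patient is 1/28 = 3.6% of the sample. The other is the estimated change: if returning for T3 depends on how the patient felt at T2, the complete-case means at every visit describe a selected group. Treatment is unblinded (section 7), so patients decide whether to return knowing both their arm and their response.

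**Working it through.** The plan gives no figure for missed visits, so there is none to reproduce. The rates below are assumptions. The 28 patients and the SD of 2.918 (placebo group, end of treatment) come from section 5.

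**1. Patients lost.** T1 and T2 are tied to sessions that a completer attends, so T3 is the main visit such a patient can miss.
- T3 only, missed at 5% or 10%: 28 × 0.05 = 1.4; 28 × 0.10 = 2.8 patients.
- Upper case, all three follow-up visits missed independently at those rates: 1 − 0.95³ = 0.143, about 4.0 of 28; 1 − 0.90³ = 0.271, about 7.6 of 28.

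**2. Precision.** The section 5 inputs are "whose standardized effect size was 0.70 assuming a one-sided alpha error of 0.05 and a beta error of 0.20". Assume 14 per arm (the ratio is not stated) and use the normal approximation, power = Φ(0.70 × √(n/2) − 1.645).
- n = 14: Φ(1.852 − 1.645) = 58.2%.
- n = 13.3 (5% lost): Φ(1.805 − 1.645) = 56.4%.
- n = 12.6 (10% lost): Φ(1.757 − 1.645) = 54.5%.

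So T3-only loss at these rates costs about 2 to 4 points of power for a comparison at T2, where no value is missing. That the starting power is 58% and not 80% is a separate sample-size matter and does not bear on this point.

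**3. Bias in the T3-only case.** Assume normal VAS with SD 2.918 and equal correlation r between visits, true changes T2-T0 and T3-T0 both −2.00, and every patient measured at T2. Half of those with T2 ≥ T0 skip T3.

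Let D = T2 − T0. Then D has mean −2 and SD s = 2.918 × √(2(1 − r)). Write p = P(D ≥ 0) and e = −2p + s·φ(2/s), which is the mean of D over the part where D ≥ 0. The share lost is p/2, and the complete-case mean of D is (−2 − e/2)/(1 − p/2).

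| r | s | p | e | Share lost | Complete-case T2-T0 |
|---|---|---|---|---|---|
| 0.5 | 2.918 | 0.2465 | 0.427 | 12.3% | −2.52 |
| 0.7 | 2.260 | 0.1881 | 0.233 | 9.4% | −2.34 |

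No T2 value is missing here, so the excess of 0.52 or 0.34 comes entirely from discarding observed data. Using every T2 value gives −2.00.

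At T3, the regression of T3-T0 on D has slope 0.5 under equal correlation. The complete-case T3-T0 is therefore −2 + 0.5 × (−0.52) = −2.26, or −2 + 0.5 × (−0.34) = −2.17. Predicting T3 from T0 to T2 over all patients, which is in effect what a likelihood-based model does, returned −2.00 in a simulation of 2,000,000 patients at each correlation.

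**4. Direction and arm comparison.** Under missing completely at random there is no bias, only lost precision. If good responders are the ones who stay away, the sign reverses. If the mechanism and response are alike in both arms, the two biases cancel in the time-by-intervention interaction. If the mechanism acts in one arm only, the spurious arm difference in T2-T0 is 0.52 or 0.34. The standard error of that difference at 14 per arm is s × √(2/14) = 1.10 or 0.85, so the extreme case is about 0.5 or 0.4 of a standard error.

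**The case against.** The strongest reply is that nothing may have gone wrong. The text is in the past tense, no missed visit is reported, and with complete data the ANOVA and a mixed model use the same patients. Listwise deletion is inferred from the named method and is not stated. All of this stands. It limits what can be said about harm, but it does not supply a rule for an incomplete patient.

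A reader might also infer more than the documents support:

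- *That patients who withdraw midway are lost through the ANOVA.* Someone who leaves after T1 misses sessions 5 to 8 and, on the natural reading of section 2, is already excluded for non-compliance. Changing the model does not bring that patient back.
- *That 14% to 27% of patients would be lost.* That needs independent misses at all three follow-up visits, two of which follow sessions a completer attends. Misses clustered in the same patients would lose fewer.
- *That the analysis is biased.* It can be. Bias requires missingness related to outcome, and bias in the arm comparison requires the mechanism or response to differ between arms.
- *That any gap removes a patient from everything.* Deletion is per outcome. A missing saliva sample alone leaves the VAS analysis intact.

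**Conclusion.** The point holds in a limited, conditional form and justifies a change to section 8. The named method keeps only patients with all four visits. A treatment completer who misses an assessment, mainly T3, is dropped from that outcome along with valid earlier values.

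At assumed T3 losses of 5% to 10%, the cost is 1.4 to 2.8 of 28 patients and a few points of power. Under one plausible outcome-related mechanism, the T2-T0 change is overstated by 0.34 to 0.52 points on the VAS. These sizes rest on the assumed missing rates, normality, equal correlation of 0.5 or 0.7, the SD borrowed from section 5 and a true change of −2.00. The documents do not show that any value was lost or that any reported result is biased.

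**What to change.** In section 8, replace the two-factor ANOVA for VAS and salivary flow with a linear mixed model:

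- SPSS MIXED with REML and fixed effects for group, visit and group-by-visit.
- Unstructured covariance over the four visits (4 × 5/2 = 10 parameters), with a small-sample degrees-of-freedom correction because there are only 28 patients. State beforehand the simpler structure to use if the model does not converge.
- Fit to all available values of every patient in the analysis set, with the Bonferroni contrasts taken from this model.
- Report the number of patients contributing at each visit, by arm and outcome. If all visits are complete, say so.
- Keep the completer ANOVA as a sensitivity analysis.

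The cost is a little more analysis work in the same software on the same data, with no new patients; where the ANOVA has already been run, this is a re-analysis. The Mauchly test is no longer needed for the main model. The downside is reliance on missing at random, which is a weaker assumption than the missing completely at random that in general protects the complete-case analysis from bias.

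Bringing back patients excluded for non-compliance would mean changing section 2 and following those patients up. That is a separate decision, which this fix does not make.
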